Appendix IV

**Joint Stiffness Assessment
(Specific to ipsilateral extremity/region)**

MC: _____

Patient Name: _____

Date of Assessment: _____

Name of Assessor: _____

Was Joint Stiffness Present: Yes/No (circle one)

If yes, Joint Affected:

- Upper proximal extremity
- Upper distal extremity (includes elbow)
- Lower proximal extremity (includes knee)
- Lower distal extremity
- Superficial trunk

Grade:

- 1- Mild stiffness; slight ROM loss
- 2 - Moderate stiffness; pain, ROM loss
- 3 - Severe stiffness, pain, ROM loss
- 4 - Necrosis; complete fixation

Attribution to RT:

- Definite
- Possible
- Probable
- Unlikely
- Unrelated

Attribution to Surgery:

- Definite
- Possible
- Probable
- Unlikely
- Unrelated

Appendix V

Regional Alopecia Assessment

MC: _____

Patient Name: _____

Date of Assessment: _____

Name of Assessor: _____

Was Regional Alopecia Present: Yes/No

If yes, Region Affected:

- Upper proximal extremity
- Upper distal extremity (includes elbow)
- Lower proximal extremity (includes knee)
- Lower distal extremity
- Superficial trunk

Grade:

- 1 - Hair loss of <50% of normal for that individual that is not obvious on close inspection
- 2 - Hair loss of >50% normal for that individual that is readily apparent to others

Attribution to RT:

- Definite
- Possible
- Probable
- Unlikely
- Unrelated

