4.0 Test Schedule

	Pre-treatment/ Baseline ≤30 days prior to registration	Hypo-fractionated RT 42.75 Gy in 15 fractions	Post-RT Assessment (+/- 5 days)	Pre- Operative Assessment Within 2 weeks of surgery⁹	Post- Operative Assessment 4-8 weeks Post-Surgery^{6,9}	Years 1 & 2 Post-Surgery Assessment Every 6 Months Post-Surgery^{7,8,9} (+/- 8 weeks)	Years 3-5 Post-Surgery Assessment Annually Post- Surgery^{7,8,9} (+/- 8 weeks)
History, physical exam ⁷ , ECOG status	X		X	X		X	X
Pathology review ¹	X				X		
Primary site MRI ² , ⁵	X			X		X	X
PET/CT or CT Chest ⁵ ,	X			X		X	X
Pregnancy test ³	X						
AE Acute Assessment (See section 10.0)	X		X	X			
Hypofractionated RT		X					
CTCAE v5.0 Solicited Late Toxicity Assessment (See section 10.0)	X				X	X	X
Wound Complication Assessment (Appendix VI/Section 11.0)					X	X	
Regional Alopecia Assessment (Appendix V)	X		X	X			
Joint Stiffness Assessment (Appendix IV)	X		X	X		X	X
PROMISE-10 ^a	X			X		X ⁴	
TESS ^b	X			X		X ⁴	

1. Pathology review includes histopathologic diagnosis of soft tissue sarcoma and grade, where applicable.
2. CT is acceptable if MRI is not advisable.
3. For women of childbearing potential only. Must be done ≤7 days prior to beginning radiation treatment. Tubal ligation and IUD in place are exceptions.
4. Obtained at 12, 18, and 24 months.
5. Within 60 days of enrollment
6. Follow Up timepoints may be evaluated outside the anticipated window as deemed appropriate by Stand of Care Radiation Oncology and Orthopedic Surgery follow up schedule
 - a. Patient-Reported Outcomes Measurement Information System
 - b. Toronto Extremity Salvage Score
7. Assessments may be completed by NP/PA in person or by virtual and/or phone visit if patient is unable to return to study site.
8. Per physician discretion
9. If patient develops any type of disease progression or is unwilling to return to the institution, patients will move to yearly survival follow up. No additional assessments will need to be done.

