10.2 Recording Adverse Events

CTCAE term (AE description) and grade: The descriptions and grading scales found in the revised NCI Common Terminology Criteria for Adverse Events

(CTCAE) version 5.0 will be utilized for AE reporting unless as otherwise stated in the table below.

All appropriate treatment areas should have access to a copy of the CTCAE version 5.0. A copy of the CTCAE version 5.0 can be downloaded from the CTEP web site:

(http://ctep.cancer.gov/protocolDevelopment/electronic_applications/ctc.htm)

10.2.1 Adverse event monitoring and reporting is a routine part of every clinical trial. First, identify and grade the severity of the event using the CTCAE version 5.0. Next, determine whether the event is expected or unexpected and if the adverse event is related to the medical treatment or procedure. With this information, determine whether the event must be reported as an expedited report (see Section 10.3).

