- 16.3.2.5.4 Second primary tumor is defined as any different histology of sarcoma or any other type of malignancy inside or outside the radiation field.
- 16.3.2.6 Adverse Events: All eligible patients that have initiated treatment will be considered evaluable for assessing adverse event rate(s). The maximum grade for each type of adverse event will be recorded for each patient, and frequency tables will be reviewed to determine patterns. Additionally, the relationship of the adverse event(s) to the study treatment will be taken into consideration. Late toxicities (as defined in sections 16.3.2.4) will be summarized separately.
- 16.3.2.7 Quality of Life Measurements – PROMIS-10: Results from the ten-item PROMIS questionnaire will be used to evaluate physical health and mental health, separately. Changes in raw score from baseline to 24-months post-surgery will be assessed, in each of the physical and mental health domains. The Wilcoxon signed-rank test will be utilized to assess changes in raw PROMIS scores. Mean change, along with standard deviation will be reported.
- A scoring table to compare this patient population to global means may be utilized for various timepoints. However, because this scoring table is prepared for a fixed set of items, it can only be used when an examinee responds to all of the items in the set. This, along with all other analyses, including graphical representations and comparisons between other timepoints or subgroups of patients may be performed, but will be considered exploratory.
- 16.3.2.8 Quality of Life Measurements – TESS: Results from the Toronto Extremity Salvage Score (TESS) questionnaire will be used to evaluate functional outcomes. The TESS specifically measures performance of activities of daily living, and is separated into upper and lower extremity versions (29 and 30 questions, respectively).
- Patients will fill out the appropriate version, and point totals will be summed. Mean change from baseline to 24 months post-surgery, along with standard deviation will be reported by version. The Wilcoxon signed-rank test will be used to assess changes in TESS scores within questionnaires. All other analyses, including graphical representations, GEE model creation, and comparisons between different timepoints or subgroups of patients may be performed, but will be considered exploratory.

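### The two grades on the Appendix V alopecia form are not exhaustive: clearly seen loss below 50%, loss of exactly 50%, and less conspicuous loss above 50% meet neither definition

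*Combined protocol and SAP*

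**What the plan says.** The Appendix V form opens with a presence item, "Was Regional Alopecia Present: Yes/No". If the answer is yes, it asks for the region affected, a grade and the attribution to radiation therapy. Only two grades are offered:

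- Grade 1: "Hair loss of <50% of normal for that individual that is not obvious on close inspection"
- Grade 2: "Hair loss of >50% normal for that individual that is readily apparent to others"

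The test schedule in section 4.0 marks the form at three points: baseline, after radiation therapy and before surgery. No post-operative or follow-up column is marked.

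For adverse events in general, section 10.2 says that CTCAE "version 5.0 will be utilized for AE reporting unless as otherwise stated in the table below". The solicited toxicity tables in section 10.4 do not list alopecia. Section 16.3.2.6 describes the adverse event summary: "The maximum grade for each type of adverse event will be recorded for each patient, and frequency tables will be reviewed to determine patterns". It does not name alopecia, and neither does any other part of section 16.

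**The concern.** A grading scale should give each patient with the condition exactly one grade. Here each grade requires two things at once, how much hair is lost and how visible the loss is, and the form does not say which prevails when they disagree. The Grade 1 visibility condition also works against the purpose of the form. An assessor who looks closely, plainly sees partial loss and answers yes to presence is shut out of Grade 1 by its wording and out of Grade 2 by the percentage.

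Assessors will settle this in different ways. Some will leave the grade blank, some will mark Grade 1 on the percentage alone, and a few may mark Grade 2 on visibility. If alopecia is tabulated by maximum grade, the split between Grade 1 and Grade 2 would then partly reflect assessor habit.

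**Working it through.** No design figure is involved, so there is nothing to reproduce numerically. The check is one of logical coverage: cross the extent of loss with its visibility, and see which combinations satisfy both halves of a grade.

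Inputs, all from Appendix V:

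- Grade 1 = loss below 50% **and** not obvious when examined closely.
- Grade 2 = loss above 50% **and** readily noticed by other people.
- There is no third grade and no tie-breaking instruction.

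| Extent of loss | Visibility | Grade as worded |
|---|---|---|
| Below 50% | Not obvious when examined closely | 1 |
| Below 50% | Obvious when examined closely | none |
| Exactly 50% | Any | none |
| Above 50% | Not readily noticed by others | none |
| Above 50% | Readily noticed by others | 2 |

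The second row matters most, because it is mild loss that the assessor can plainly see. The exactly-50% row is a boundary omission (strictly below against strictly above). The fourth row may be uncommon; the documents give no frequency for any row.

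Does anything elsewhere close the gap? Section 10.2 makes CTCAE v5.0 the default unless a table says otherwise. Alopecia is in none of the section 10.4 tables, and Appendix V prints its own grades without saying whether they replace CTCAE. The documents do not reproduce the CTCAE text, so the two cannot be compared here. The gap stays open.

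What uses the grade?

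- **Objectives and primary endpoint** (sections 2.0 and 16.1.1): alopecia is not mentioned, and the primary endpoint is major wound complications.
- **Late toxicity of grade 2 or above** (section 16.3.2.4): the window opens 3 months after radiation therapy. Section 7.2 requires surgery within 6 weeks, plus or minus 1 week, so at most 6 + 1 = 7 weeks after radiation therapy. For a patient treated to schedule, the last alopecia form precedes surgery and so falls before the window opens.
- **Stopping rule** (section 16.4.2): it counts events of Grade 3 and above, and Grade 5 events. This scale ends at Grade 2.
- **Adverse event tables** (section 16.3.2.6): the general wording could take in alopecia. This is the only route by which the gap reaches a reported result.

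**The case against.** The strongest reply is that the percentages separate the grades well enough in practice. An assessor who sees loss clearly below 50% would most plausibly mark Grade 1, and marking Grade 2 would contradict its own threshold. Loss above 50% that others readily notice is still graded correctly. This is fair and limits the likely damage, but it relies on the assessor setting aside half of the printed definition, and nothing on the form says to do so.

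A reader might go further and infer any of the following. The documents do not support them.

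- *The form cannot record mild alopecia.* It can. Presence, region and attribution are separate items; only the grade is undefined.
- *Grade 1 describes something no examiner could observe.* The condition is that the loss is not obvious, which is weaker than not visible. Subtle but detectable loss below 50% still fits Grade 1.
- *The Grade 1 and Grade 2 frequencies are uninterpretable.* This is not shown. The documents do not say how many patients would fall in the gaps, or that clearly seen loss below 50% is the usual mild presentation.

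It is also fair to say that applying section 16.3.2.6 to this form is an inference, since that section does not name alopecia. A word lost when the PDF was read cannot be wholly excluded, although the Grade 1 sentence reads as unbroken.

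**Conclusion.** The point holds as a minor drafting defect on an ancillary form. As worded, three combinations of extent and visibility have no grade, and the lowest grade excludes mild loss when it is clearly seen. The consequence is confined to possible inconsistency between Grade 1 and Grade 2 in any descriptive adverse event table that includes alopecia. No objective, named endpoint, power figure or stopping decision is touched.

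The size in patients cannot be given, because the documents state no expected alopecia rate or distribution of extent. The conclusion rests on reading the two definitions literally, on the printed text being complete, and on alopecia being tabulated by grade at all.

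**What to change.** Reword the two grades in Appendix V so that percentage alone decides and every extent of loss is covered:

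- Grade 1: any loss below 50% of normal for that person.
- Grade 2: loss of 50% or more.

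Keep the visibility phrases only as descriptive guidance. Simply reversing the Grade 1 visibility phrase, so that it requires loss seen on close examination but not readily noticed by others, would not be enough. Loss below 50% that others do notice, and loss of 50% or more that they do not, would still have no grade.

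State in Appendix V or section 10.2 whether the form's own scale or CTCAE v5.0 governs alopecia, and in section 16.3.2.6 whether alopecia is included in the adverse event tables.

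For completed forms, query those marked yes for presence with no grade, and regrade only where source notes allow. The form has no field for percentage lost or for visibility, so it cannot support regrading by itself. Cases that cannot be resolved should be reported as present, grade unknown.

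The cost is a short form correction, a clarifying sentence or two and a limited set of queries. The one real downside is that some earlier forms will remain ungraded. Nothing in the design, sample size or treatment changes.

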Appendix VI

Surgical Wound Complication Assessment

MC: _____

Patient Name: _____

Name of Assessor: _____

Surgical wound complication: Yes/No

If yes,

Surgical wound start date: _____

Surgical wound end date: _____

Date notified of surgical wound complication: _____

Surgical wound complication classification:

- Wound management via secondary unplanned operation under anesthesia
- Wound management via invasive procedures other than operation

Surgical wound complication procedure performed: _____
